Document: Protocol and SAP

Study title: Neuronal and Behavioral Effects of Implicit Priming in Obese Individuals

NCT: NCT02347527

Document date: 7/02/2015

COMIRB Protocol

COLORADO MULTIPLE INSTITUTIONAL REVIEW BOARD
[name] [contact] [contact]

Project Title (COMIRB): Effects of implicit priming on food cue responses

Principal Investigator: [name]

Co-Investigator: [name].

Version date: 7/02/15

I. Hypotheses and Specific Aims:

The development of novel strategies to promote weight loss and maintenance is critical, given the increasing prevalence of obesity in the United States. Greater responsiveness to high-calorie foods may lead to greater intake of these foods, contributing to obesity. The main aim of the current pilot project is to inform the development of a potential weight loss tool by assessing how priming pictures of food affects ratings. To achieve this goal, participants will be assigned to either the (a) active group or (b) control group. In the active group, images of high- and low-calorie foods will be paired with implicitly presented (below perceptual threshold) images of either negative or positive valence (high-calorie paired with negative; low-calorie with positive). For example, an ice cream image primed with an image of a pizza with cockroaches on it, or a piece of fruit primed with an image of a smiling child. During this task, participants will not perceive these primed pictures (although they will be told that they are there), and will rate each food picture on whether the food is "healthy" or "not healthy". Those in the control group will be primed with neutral images. Brain responses to food pictures will be recorded before and after the priming task. Participants will rate pictures of foods before and after the priming task on how much they "desire to eat" each food. In addition, participants will eat a buffet-style breakfast and lunch after the priming task, to see how the task affects food intake.

II. Background and Significance:

The prevalence of obesity in the United States has drastically increased in recent decades¹, creating a significant health concern. Current estimates indicate that 34% of adults are obese and 68% are either overweight or obese². Weight loss in obese individuals is associated with a reduction in comorbid conditions, such as cardiovascular disease and hypertension³. The development of novel and effective strategies that promote healthier eating habits could be helpful in weight maintenance.

Previous studies, including those from our laboratory, have found neuronal responses to visual food cues to be heightened in overweight/obese⁴⁻⁷, reduced-obese^{6, 8-10}, and obese-prone¹¹ compared to lean individuals. Greater responsiveness to high-calorie foods may lead to greater intake of these foods and subsequently, contribute to obesity. Supporting this, previous studies have found overweight/obese individuals to demonstrate greater activation to high-calorie food cues (compared to low-calorie food cues) in comparison to lean individuals⁵. Behavioral studies have found similar results: overweight/obese individuals have been found to rate high calorie foods as more appealing compared to lean individuals^{5, 10}, being overweight/obese has been associated with increased fat and sweet preferences^{12, 13}, and preference for snack foods has been associated with future weight gain¹⁴. Food preferences are thought to be largely learned responses¹⁹ that develop via classical conditioning through repeated pairings with positively and negatively valenced stimuli²⁰, which can influence food preferences and intake¹⁹. Indeed, implicit (automatic) attitudes towards food have been

associated with self-reported snack consumption and food choices^{21, 22}. Thus, changing these automatic associations may alter food preferences and intake.

The proposed study is the first step in a larger goal to identify a technique to promote healthier eating that would neuronal responses to food cues and food intake behaviors. This pilot study will investigate an implicit priming task, in which positive or negative images are presented immediately prior to food images, but are not consciously perceived. This pilot study will identify whether implicit priming can alter ratings of food pictures on “desire to eat.” In addition, we will assess how priming alters brain responses to food and food intake. The results of this study will inform the development of a larger study to implement this approach as an intervention to promote healthier eating habits.

Previous studies have found implicitly pairing target pictures with pictures or words of positive/negative valence (e.g., pairing a flower picture with the word “stench”) lead to increased liking/disliking of the target picture²³. These effects may be quite durable, as one study found alterations in ratings of target pictures to remain 2 months later²⁴. As such, this approach has the potential to reduce the appeal of hedonic foods and increase the appeal of healthier foods, which could encourage reduced intake of high-calorie foods in favor of low-calorie foods, promoting weight loss and weight loss maintenance.

III. Preliminary Studies/Progress Report:

As this is a pilot study, there are no preliminary data to report. If the aims of the project are achieved, the next step would be to use the results to inform development of an intervention to promote healthy eating. The subsequent study will also investigate the effects of this intervention on neuronal responses and subsequent food intake.

IV. Research Methods

A. Outcome Measure(s):

Primary outcomes in this study will be:

- 1) Ratings of food pictures on “desire to eat”
- 2) Brain responses to food pictures
- 3) Food intake

B. Description of Population to be Enrolled:

The study will include adult participants between ages 21-65. Participants older than 65 years of age will not be included to avoid potential effects of aging on food perceptions.

Exclusion criteria include: history of major medical condition affecting weight/metabolism; medications affecting weight; pregnancy; bariatric surgery; history of psychiatric/eating disorder; current dieting; those following a vegan or vegetarian diet; and fMRI exclusions (claustrophobia, metal in body, weight>300 lbs). Those at risk for eating disorders (score >20 on the Eating Attitudes Test [EAT-26]) will also be excluded.

C. Study Design and Research Methods

Initially, subjects will be pre-screened over the phone to assess eligibility. Eligible and interested subjects will be asked to arrive to the screening visit in a fasted. Following informed consent and demographics, participants will undergo a screening day including baseline measures and a 1-day, run-in eucaloric diet, prior to the fMRI study day. The run-in diet's caloric value will be

determined through body composition measurements taken at baseline, using BodPod. Also during the initial baseline visit, participants will be asked to complete several food/eating-related questionnaires: Eating Attitudes Test (EAT-26), Disgust Scale -R, Three Factor Eating Questionnaire (TFEQ), Power of Food Scale (PFS), and Food Craving Inventory (FCQ). In addition, participants will complete two brief surveys, one in which they will rate food pictures on “desire to eat” and another in which they will categorize foods as “healthy” or “unhealthy.” After baseline measurements, participants will be randomly assigned to either the (a) active group or (b) control group in a 1:1 ratio. In the active group, images of high- and low-calorie foods will be paired with implicitly presented (below perceptual threshold; presented for 20 ms) images of either negative or positive valence (high-calorie paired with negative; low-calorie with positive). During this task, participants will not perceive these primed pictures (although they will be told that they are there), and will rate each food picture on whether the food is “healthy” or “not healthy.” Those in the control group will be primed with neutral images. The priming task will be completed during functional magnetic resonance imaging (fMRI), to assess brain responses during the task. Additionally, participants will view a series of food pictures during fMRI recording immediately before and after the priming task. Following the priming/categorization task, participants will again complete the food picture ratings outside the MRI. Following this, participants may stay for an additional 4 hours, across which they will consume a buffet-style lunch to measure food intake. Subjects will also complete visual analog scale (VAS) ratings on their subjective hunger, fullness, and prospective food consumption at baseline, prior to, and 30/60 minutes after each ad libitum meal. The entire session will take approximately 2-6 hours. Participants may also be asked to return 3-5 days later to complete the food picture ratings again, which will take approximately 10 minutes.

D. Description, Risks and Justification of Procedures and Data Collection Tools:

Ad-Libitum Food Intake: Ad-libitum intake will be measured during a lunch meal served after the fMRI priming task. The purpose of this method will be to use weigh and measure methods to quantify food intake and macronutrient content of the diet directly. Specifically, a research dietitian will work with the subject to provide meals that replicate, to the extent practical/possible, usual meals consumed by the subject. Subjects will be asked to not consume any other food or beverages and to maintain usual activities. All meals will be prepared by the metabolic kitchen of the Anschutz Health and Wellness Center (AHWC) and will be offered with 30% more food than predicted requirements. Subjects will be instructed to eat what they want and that they can request more of any food. This design should neither restrict intake, nor encourage over consumption. Food intake and macronutrient composition will be determined by ‘weigh and measure’ methods by the dietary staff of the AHWC.

Body composition: Fat mass and fat-free body mass will be measured at baseline, prior to the fMRI study day, using BodPod at the AHWC. The BodPod system employs air displacement plethysmography to determine body composition, through calculating body volume and measuring body mass³³.

Demographic measures: Participants will be asked to report their age, ethnicity, and body mass index (see “Demographics Form” attachment). A potential risk is discomfort at disclosing this information. It will be made clear that participants can choose not to disclose any of this information if they are not comfortable doing so.

Eating-Related Questionnaires: TFEQ to measure food-related behaviors including restraint, disinhibition, and hunger²⁹; PFS to assess the drive to eat palatable foods in the absence of

energy need or “hedonic hunger”³⁰; FCQ to assess food-related cravings³¹; Disgust Scale-R to measure disgust; and EAT-26 to assess risk for eating disorders³².

Food rating task: For the food ratings, images of foods will be rated for “desire to eat” on a visual analogue scale from 0-100 (with 0 indicating “no desire to eat” and 100 indicating “strong desire to eat”). The food rating task will be performed using the ImageRate program²⁸ and includes 90 food pictures, which takes approximately 10 minutes. This will be repeated both before and after the priming categorization task, and again 3-5 days following the initial session. A potential risk during this procedure could be fatigue. However, given that each iteration of this task is only 10 minutes, this risk is anticipated to be minimal. To mitigate this risk, participants are given a short break between each of the three 10-minute portions of the experiment.

Priming/categorization task: In the active group, images of high- and low-calorie foods will be paired with implicitly presented (below perceptual threshold; presented for 20 ms) images of either negative or positive valence (high-calorie paired with negative; low-calorie with positive). For example, an ice cream image primed with an image of cockroaches on food, or a piece of fruit primed with an image of a smiling child. The negative and positive images used for priming were taken from the International Affective Picture System (IAPS; csea.phhp.ufl.edu), which is a large set of standardized color photographs ranging across a wide variety of categories. These pictures have been rated for emotional valence. We will exclude the most emotionally arousing negative pictures to avoid using images that could make participants overly uncomfortable, so will only use those with an arousal rating of less than 7. During the task, participants will not perceive these primed pictures (although they will be told that they are there), and will rate each food picture on whether the food is “healthy” or “not healthy,” as fast as possible. Those in the control group will be primed with neutral images and will also rate the food pictures as “healthy” or “not healthy.” The task will be performed during fMRI recording using Eprime 2.0, which will allow us to collect reaction time and response data for the response to each picture. The entire task takes approximately 10 minutes. As with the rating task, a potential risk of this procedure is fatigue. As with the rating task, this task is also only 10 minutes, so minimal risk of fatigue is anticipated. To mitigate this risk, participants are given short breaks between portions of the experiment. In the unlikely event of a computer malfunction, there is a very small potential risk that the screen may pause on one of the priming images (which are usually not perceived). If this were to happen on an image of negative valence, there is potential for the participant to be uncomfortable if it were an image they found to be unpleasant (e.g., cockroaches on food). The computer used to present the stimuli has been tested extensively to ascertain that it is fast and powerful enough to complete the paradigm with no pauses. In 30 test runs, the computer has not once paused during picture presentation. We have also used a high-speed video camera (with slow motion playback) to ascertain that the computer being used is presenting the priming stimuli for 20 ms, as desired. There are no known risks to the types of magnetic fields and radio waves that are used in functional MRI studies. However, some types of metal may be moved or may heat up by the magnets in the MR scanner. The MRI machine is a small round tube. Subjects with claustrophobia may feel uncomfortable. Very rarely, some people experience warmth and reddening of the skin. This usually goes away after a few minutes. As such, we feel that the risks are minimal.

Run-In Diet: A 1-day eucaloric, run-in diet will be performed prior to the study day. The caloric value of the diet will be determined by taking into account measured resting energy expenditure (REE) and lean body mass (LBM; multiplying by a correction factor to adjust for physical activity) and will have a macronutrient composition of 50% carbohydrate, 30% fat, and 20% protein. This baseline dietary control period will ensure energy balance and weight maintenance

prior to studies being performed. This approach has been used effectively by our group in a number of prior studies. All meals will be prepared by the metabolic kitchen of the AHWC.

Visual food cues task: Visual stimuli will be presented during fMRI recording using a projector and screen system. fMRI will be performed while subjects view food images (48 high-calorie, 48 low-calorie). Two runs each lasting approximately 6 minutes will be performed. Each run will consist of a blocked design with 6 blocks of high-calorie food images, 6 blocks of low-calorie images, and 6 blocks of non-food-related objects. Runs will also include 6 blocks of a low-level baseline fixation condition, consisting of 3 crosses centered in a black screen. This task will be completed before and after the intervention and will take approximately 8 minutes each time.

E. Potential Scientific Problems:

This is a pilot study designed to identify the feasibility of using implicit priming as an intervention to promote healthier eating. As study utilizes two simple behavioral measures, and fMRI measurement during a visual food cues task we have used in multiple previous studies, there are no anticipated scientific problems.

F. Data Analysis Plan:

Response and reaction time data for the response to each picture during the priming task will be collected via the presentation software (Eprime 2.0). These data will be imported into SPSS version 21 (IBM Corp., Armonk, NY). Responses will be split into high- and low-calorie foods, which will be compared using paired-samples t-tests. The food ratings are performed using the ImageRate program ²⁸, which saves results in a spreadsheet. These ratings (for pre- and post-priming) will be imported into SPSS and split into high- and low-calorie foods. The change between session 1 and session 2 will be assessed for both high- and low-calorie foods using paired-samples t-tests. Group comparisons (control vs. active) will use independent-samples t-tests and the interaction between high- and low-calorie foods (difference in the change between each category) will also be tested.

fMRI data will be processed with Statistical Parametric Mapping (SPM8, Wellcome Dept. Cognitive Neurology) in Matlab 7.14. All data initially will be visually inspected for motion, field homogeneity and reconstruction errors, at least bi-weekly to ensure that scans with poor quality can be replaced. We typically observe excess movement (> 2 mm) in 1 out of every 15 scans. Data from each participant will be realigned, normalized to the Montreal Neurological Institute (MNI) template using a gray-matter-segmented IR-EPI as an intermediate, and smoothed with an 8-mm full width at half maximum Gaussian kernel to improve signal-to-noise ratio and account for non-independence on neighboring voxels. After preprocessing, a 128-second high-pass filter will be applied to remove low-frequency fluctuation in the BOLD signal. To account for intersubject/intrasubject variability, a random effects statistical model will be utilized. To generate this model in SPM8, statistical parametric maps will be generated for each subject using the general linear model to describe data variability on a voxel by voxel basis. The hemodynamic response will be modeled with a double gamma function, without temporal derivatives. Hypotheses expressed in terms of model parameters will be assessed at each voxel with univariate statistics, yielding an image whose voxel values comprise a statistical parametric map⁴⁷. For visual food cues tasks (pre- and post-intervention), first-level parametric maps will be entered into a second-level repeated measures ANOVA, in which group effects (change in high-calorie>objects and basics>objects from pre- to post-intervention) will be examined with directional t-contrasts. For correlations noted above, % signal change reflecting activity for each participant will be extracted at the local maximum for each region of interest (insula/ventral

striatum). Relationships between change in neuronal response during the visual food cues task from pre- to post-intervention and (1) eating behaviors, (2) body composition, and (3) neuronal response during IP will be determined using correlations in SPSS version 21.0 (IBM Corp., Armonk, NY), as will the relationship between neuronal response during IP and subsequent eating behaviors. Differences in eating behavior measures between groups (IP vs. control) will be performed using independent samples t-tests in SPSS.

G. Summarize Knowledge to be Gained:

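### Food intake is a primary outcome, but the protocol conflicts with itself on whether every participant has the intake meal, which meals count and what kind of meal is served

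*Combined protocol and SAP*

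**What the plan says.** Section IV.A introduces a list of three with "Primary outcomes in this study will be"; food intake is the third.

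On attendance, section IV.C (Study Design and Research Methods) says: "Following this, participants may stay for an additional 4 hours, across which they will consume a buffet-style lunch to measure food intake". It adds: "The entire session will take approximately 2-6 hours". Section I says "participants will eat a buffet-style breakfast and lunch after the priming task, to see how the task affects food intake". Section IV.D (Ad-Libitum Food Intake) states, with no condition, that intake will be measured at a lunch after the priming task.

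On which meals count, section I therefore has two meals, and IV.C and IV.D have one. Yet IV.C also schedules the appetite VAS ratings at baseline and "prior to, and 30/60 minutes after each ad libitum meal", which is wording for more than one meal.

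On format, sections I and IV.C describe a buffet. Section IV.D has a dietitian providing meals that resemble, as far as practical, what that participant usually eats.

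On measurement and analysis, section IV.D specifies weighing and mentions both intake and macronutrient composition. Section IV.F assigns independent-samples t-tests to differences in eating behaviour between the groups. It names no unit, no set of meals and no single summary.

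**The concern.** A primary outcome should be obtained in the same way from everyone randomised. Here two separate things are unsettled.

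First, the stay comes after randomisation and after priming. If it is optional, some participants will have no value for a primary outcome, precision is lost, and a comparison restricted to those who stayed need not preserve the randomised groups. The plan does not say who stays or how missing intake is handled.

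Second, and whatever is decided about attendance, staff following section I and staff following section IV.D would add up different meals under the same outcome name. The meal format matters too. The rationale in section II is that priming "could encourage reduced intake of high-calorie foods in favor of low-calorie foods". A shift of that kind is comparable between participants only if they are offered a comparable selection. Meals built around each person's usual diet would not guarantee that.

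**Working it through.** The plan states no figure for food intake (no sample size, power, SD or staying rate), so there is nothing to reproduce. The check is a comparison of text with one piece of arithmetic.

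**Attendance.** Inputs, both from IV.C: additional stay 4 h; session about 2 to 6 h. The spread is 6 − 2 = 4 h, exactly the additional stay, and 6 − 4 = 2 h, exactly the lower end. The lower end is reachable only without the stay. This favours the reading that the stay is optional.

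**Meals and format, side by side.**

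| Section | Attendance | Meals after priming | Format |
|---|---|---|---|
| I | unconditional | breakfast and lunch | buffet |
| IV.C | permissive | lunch, but VAS wording implies several | buffet |
| IV.D, Ad-Libitum Food Intake | unconditional | lunch | modelled on usual meals |

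The VAS schedule inherits the conflict. Taking baseline as one rating and 30 and 60 minutes as two, each meal adds 1 + 2 = 3 ratings, so one meal gives 1 + 3 = 4 ratings and two meals give 1 + 6 = 7.

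**Illustrations only.** Every input below is assumed, and the conclusion does not rest on any of them.

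- *Lost precision.* If a fraction f stays in both arms, the SE is multiplied by 1/√f: 1.05 at f = 0.9, 1.12 at 0.8, 1.41 at 0.5.
- *Possible bias.* Let ρ be the correlation between the propensity to stay and intake, and m(p) the standard normal density at the p quantile divided by p. The bias in SD units is ρ × [m(p₂) − m(p₁)]. With 80% against 70% staying it is 0.029 (ρ = 0.2) to 0.073 (ρ = 0.5). With 80% against 60% it is 0.059 to 0.147. It is zero in this model if staying is equal in the two arms or if ρ = 0.
- *Covariate adjustment.* If baseline fat-free mass correlates r with intake, the variance ratio net of estimating the slope is (1 − r²)(N − 3)/(N − 4). For N = 40: 0.91 × 37/36 = 0.935 at r = 0.3, a cut of 6.5%, and 0.64 × 37/36 = 0.658 at r = 0.6, a cut of 34.2%. For N = 80 the cuts are 7.8% and 35.2%. Adjustment loses a little only if r is below √(1/(N − 3)), which is 0.164 at N = 40 and 0.114 at N = 80.

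**The case against.** The best defence on attendance is that the permissive verb is loose drafting. The sentence in IV.C that says participants may stay also says they will consume the lunch, and the session length is only approximate. The same section is loose elsewhere: it says "Participants may also be asked to return 3-5 days later to complete the food picture ratings again", where section IV.D (Food rating task) says of the same ratings "This will be repeated both before and after the priming categorization task, and again 3-5 days following the initial session". If that is the explanation, the three sections agree that everyone eats the lunch, and only the wording needs tidying. This stands as a possibility. The consent form is not part of the document reviewed and may settle it. The defence does not touch the conflict over meals or over format, which remains on either reading.

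A reader might infer that the intake comparison is biased. The document does not support that. Bias would need staying to be related both to arm (or to the effect of priming) and to intake. Neither is shown, and primes shown for 20 ms, below perceptual threshold, make it unlikely that participants know their arm.

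A reader might also infer that the eating-behaviour comparison in IV.F could mean the eating questionnaires and not intake. That is weak. Section IV.C places those questionnaires at the baseline visit, before random assignment, and schedules no repeat, and the preceding sentence of IV.F concerns eating behaviour that follows the priming. The t-test most naturally refers to intake. What is missing is the unit and the meals to be summed.

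Finally, this is a pilot, and the edits are mostly wording. That is fair, but intake is listed as primary and the results are meant to shape a larger study.

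**Conclusion.** The point holds in this form: for a listed primary outcome, the protocol conflicts with itself on which meals count and on the format of the meal, and its more natural reading lets a randomised participant finish without being measured. Confidence is highest for the meal conflict, which depends on no interpretation. The attendance reading is favoured by the protocol's own session length but could be a drafting slip.

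The effect cannot be sized from the document. No bias is demonstrated, and the illustrative figures above carry no weight for how serious this is. The absence of a unit and of a missing-data rule would, taken alone, be missing detail; both are best settled when the conflicting sections are reconciled. The unadjusted t-test is valid in a 1:1 randomised comparison, so adjustment for fat-free mass is an improvement on offer and not the repair of an error.

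**What to change.** 1. **Attendance.** Reconcile sections I, IV.C and IV.D so that the post-priming intake measurement is part of the visit for every randomised participant. Analyse by assigned arm, report the number with missing intake by arm, and state how missing intake is handled. If the stay must remain optional, either fix who will stay before randomisation or do not list intake as primary.
2. **Meals.** Reconcile which meal or meals count and whether the format is a buffet or modelled on usual meals, and match the VAS times to the result.
3. **Variable.** In IV.F, name food intake and one primary variable, for example total kcal over the counted meals. Use kcal from high- versus low-calorie items as a secondary variable only if the reconciled format offers participants a comparable selection.
4. **Separately, for precision.** Analyse intake with a linear model on arm plus baseline fat-free mass, which BodPod already provides. The support for a useful correlation is indirect: section IV.D scales the food offered to predicted requirements without saying how these are derived, and bases the run-in diet partly on lean body mass.

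**Cost.** Protocol wording, and consent wording if it describes the stay as optional; up to 4 more hours for participants who would have left; kitchen and staff time; and classification of the weighed items if the secondary variable is used. The covariate needs no new data. The choices should be fixed before any intake data are seen.

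### Food intake, a primary outcome with no pre-priming measurement, is compared by an unadjusted t-test, and the plan names no use for the baseline hunger rating that could sharpen it

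*Combined protocol and SAP*

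**What the plan says.** Section IV.A lists three primary outcomes: desire-to-eat ratings of food pictures, brain responses to food pictures, and food intake. Section IV.D (Ad-Libitum Food Intake) measures intake at a lunch served after the priming task. No intake is measured before priming.

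On appetite, IV.C states: "Subjects will also complete visual analog scale (VAS) ratings on their subjective hunger, fullness, and prospective food consumption at baseline". It asks for the same ratings again ahead of every ad libitum meal, and half an hour and an hour afterwards. The day of the baseline rating is not given. On allocation, the same section states: "After baseline measurements, participants will be randomly assigned to either the (a) active group or (b) control group in a 1:1 ratio".

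In IV.F, the only between-group analysis that covers intake is: "Differences in eating behavior measures between groups (IP vs. control) will be performed using independent samples t-tests in SPSS". For the picture ratings, "The change between session 1 and session 2 will be assessed for both high- and low-calorie foods using paired-samples t-tests", followed by: "Group comparisons (control vs. active) will use independent-samples t-tests and the interaction between high- and low-calorie foods (difference in the change between each category"). Neither analysis has a covariate. IV.F does not mention the hunger, fullness or prospective-consumption ratings as covariate, outcome or correlate. It gives no sample size, standard deviation or correlation, and Section III says that there are no preliminary data.

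**The concern.** How much a person eats at a free meal varies widely between people, and hunger before the session is a plausible reason for part of that. For most outcomes a trial can remove stable differences between people with the outcome's own baseline value. Intake has none here, so another pre-priming variable is the only route to a covariate. The protocol appears to collect one, but the analysis plan does not take it up.

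At stake is the width of the confidence interval for intake in a pilot meant to inform a larger study. Precision may be scarcer for this outcome than for the others, because IV.C says only that participants may stay for the lunch, so fewer people may contribute intake data than were randomised. A covariate named in advance also removes the temptation to choose one after seeing the data.

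**Working it through.** The documents state no figure to reproduce. Everything below rests on assumed correlations and sample sizes.

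**Inputs.** From the documents: two arms, 1:1 allocation, intake measured only after priming, picture ratings measured before and after. Assumed: ρ, the within-arm correlation of pre-priming hunger with intake, from 0.1 to 0.5; total N of 20 or 40; r, the pre-post correlation of picture ratings, from 0.5 to 0.8, with equal SDs at both times.

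**Intake.** ANCOVA on one covariate multiplies the variance of the arm difference by 1 − ρ². Estimating the slope adds a factor (N − 3)/(N − 4), which is 17/16 at N = 20 and 37/36 at N = 40.

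| ρ | 1 − ρ² | net ratio, N = 20 | net ratio, N = 40 |
|---|---|---|---|
| 0.1 | 0.99 | 1.052 | 1.018 |
| 0.2 | 0.96 | 1.020 | 0.987 |
| 0.3 | 0.91 | 0.967 | 0.935 |
| 0.4 | 0.84 | 0.892 | 0.863 |
| 0.5 | 0.75 | 0.797 | 0.771 |

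For ρ from 0.3 to 0.5, the net reduction is therefore about 3% to 20% at N = 20 and about 6% to 23% at N = 40. In equivalent participants, 1/0.967 to 1/0.797 is about 3% to 25% more people at N = 20. Without the small-sample cost, 1/0.91 to 1/0.75 would give 10% to 33%.

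Break-even: setting (1 − ρ²)(N − 3)/(N − 4) = 1 gives ρ = √(1/(N − 3)). That is √(1/17) = 0.24 at N = 20 and √(1/37) = 0.16 at N = 40. Below these values adjustment costs a little precision: about 5% in variance at N = 20 and ρ = 0.1.

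**Picture ratings.** I read the group comparison in IV.F, from its context, as a comparison of pre-to-post change. If hunger correlates a with the pre rating and b with the post rating, its correlation with the change is (b − a)/√(2(1 − r)).

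- a = b = 0.4: correlation 0, gain 0%.
- a = 0.4, b = 0.3: gain 1.0% (r = 0.5) to 2.5% (r = 0.8).
- a = 0.4, b = 0.2, or the reverse: gain 4% (r = 0.5) to 10% (r = 0.8).

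The baseline rating itself does better. The variance is 2(1 − r)SD² for the change score and (1 − r²)SD² for ANCOVA on the baseline rating, a ratio of (1 + r)/2. That is 0.75, 0.85 and 0.90 at r = 0.5, 0.7 and 0.8, or 25%, 15% and 10% lower variance before the small-sample factor. With that factor at N = 20, 0.75 × 17/16 = 0.797 and 0.90 × 17/16 = 0.956, so a gain remains across this range.

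**The case against.** The strongest case against is that this is a valid analysis of a pilot and that the gain may be negligible. Validity is conceded. A reader might infer that a chance imbalance in hunger biases the intake comparison. It does not: under randomisation such imbalance is already in the standard error of the t-test, so it is the same precision loss seen from another side.

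The size of the gain is also fairly challenged. No correlation is documented, and several features could weaken it. The one-day eucaloric run-in may narrow the spread of hunger. Lunch follows two scanning tasks, the priming task and the picture ratings. Section I also mentions a breakfast after priming, which, if served, would come between the rating and lunch. These points stand, and are why the result is given as a range with a break-even. On the other side, IV.D claims energy balance and weight maintenance for the run-in, not equal hunger, and IV.C asks for fasting only at the screening visit.

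Three stronger readings are tempting, and the documents do not support them.

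- A reader might infer that the hunger ratings are never used. IV.F does not name them, but its eating behavior measures are undefined and could include them as an outcome.
- A reader might infer that the picture ratings lose as much as intake. They are analysed as change, so a stable hunger effect cancels.
- A reader might infer that the covariate is certainly in hand. The sentence on these ratings sits in the description of the fMRI session, but elsewhere in IV.C and IV.D baseline means the screening visit. A screening-day rating may predict the study-day lunch only weakly.

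Finally, body composition and the eating questionnaires are also measured at baseline and could predict intake. The documents do not rank these candidates. Hunger is a reasonable choice; the firmer point is that a pre-priming covariate should be named in advance.

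**Conclusion.** The point holds as a minor matter of efficiency, chiefly for food intake. The plan names no use of the baseline hunger rating and leaves a primary outcome without any covariate. With an assumed correlation of 0.3 to 0.5 and an assumed N of 20 to 40, adjustment would bring a small to moderate net gain. With a weak correlation it would bring none, or a slight loss. For picture ratings, the better covariate is the baseline picture rating, and hunger adds about 0% to 10% to the change-score analysis in the scenarios tried. The planned t-tests remain valid, and nothing here calls the trial's conclusions into question.

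**What to change.** In IV.C, state that the baseline appetite rating is taken on the fMRI day before the first scan. If it is now taken only at screening, this adds one short rating to the session.

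In IV.F:

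- Replace the intake t-test with ANCOVA on arm plus pre-priming hunger.
- Replace the between-group t-test on rating change with ANCOVA of the post-priming rating on arm plus the baseline rating, for high- and low-calorie foods, with hunger optional. Treat the difference between the two food categories in the same way.
- State that no appetite rating taken after priming is a covariate, since priming could affect it. This covers the pre-meal and the 30- and 60-minute ratings.
- Say how those later ratings are analysed, and define eating behavior measures.

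The cost is a few sentences, at most one brief extra rating, and one degree of freedom per covariate.
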